#### **4.1.2. Phase 2 Dose Expansion**

The Phase 2 Dose Expansion portion of the study will consist of 2 randomized cohorts. Subjects will be assigned randomly to a Phase 2 cohort and will be assigned 1 of 2 starting doses or schedules based on SRC evaluation of safety data, and any PK, pharmacodynamic, and efficacy data obtained during the Phase 1 Dose Escalation portion of the study. Approximately 32 evaluable subjects are anticipated to enroll in Phase 2, with up to 16 evaluable subjects per expansion cohort.

#### **4.1.3. Phase 1 Intra-Patient Dose Escalation**

Phase 1 subjects who have advanced beyond their DLT evaluation window will be offered the opportunity to escalate to a subsequent dose level that has been deemed safe by the SRC. Once the SRC has chosen the two doses for the Phase 2 expansion, Phase 1 subjects continuing treatment will be offered the opportunity to be randomly assigned to one of these Phase 2 doses, if considered appropriate by the Investigator. Subjects must have demonstrated compliance as well as a safe and favorable toxicity profile to participate in intra-patient dose escalation.

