### **9.1.2. Phase 2 Dose Expansion**

In the Phase 2 portion of the study, up to 16 evaluable subjects will be randomized into each of 2 expansion dose cohorts and evaluated for efficacy using a Simon 2-stage minimax design to exclude a response rate of < 10%, where response is defined as having  $\geq 50\%$  reduction in PSA. The hypothesized response rate under treatment is  $\geq 40\%$  and will be evaluated using a one-sided type I error rate of 0.025 with 80% power. A total of 9 subjects per dose level will be randomly assigned in Stage 1. If at least 2 responses of  $\geq 50\%$  reduction in PSA are observed, the dose level will proceed to Stage 2. If at least 5 responses are observed in a total of 16 subjects per dose level, the null hypothesis will be rejected.

Randomized dose assignment will proceed when both cohorts are open for enrollment. If one of the dose levels is closed due to safety findings or lack of efficacy findings, or is paused until Stage 1 efficacy is observed, non-randomized assignments may proceed within the open dose level expansion cohort. This hypothesis will require a dose cohort total of 16 for a Phase 2 Dose Expansion study total of 32 subjects.

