## **9.2. Populations for Analysis**

The DLT-evaluable Population is defined as all subjects in the Phase 1 Dose Escalation part of the study who receive ONCT-534 and either complete the 28-day DLT observation period or discontinue the study early due to a DLT. Subjects will be grouped by the dose received.

The Safety Population is defined as all subjects who receive at least one dose of ONCT-534. Subjects will be grouped by the ONCT-534 dose received at study entry.

The Efficacy-evaluable Population is defined as all subjects who receive ONCT-534 and complete at least one post-treatment disease assessment and do not discontinue due to clinical evidence of disease progression without documentation prior to obtaining post-treatment disease assessment. Subjects will be grouped by dose received.

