### 9.5.2. Analysis of Simon 2-stage Design

The Phase 2 Dose Expansion portion of the study will consist of 2 dose cohorts. Subjects will be assigned randomly to each Phase 2 cohort, evaluating a dose or schedule chosen by the SRC based on their evaluation of safety data and any PK, pharmacodynamics, and efficacy data obtained during the Phase 1 Dose Escalation portion of the study. Approximately 32 evaluable subjects are anticipated to enroll in Phase 2, with up to 16 subjects randomly assigned each of the 2 dose cohorts. There will be 9 subjects assigned in the first stage of the Simon 2-stage design, with the remaining 7 subjects also being assigned within a dose cohort to complete the second stage of the Phase 2 Dose Expansion portion of the study.

After evaluating the first 9 subjects for efficacy (defined as a reduction in PSA levels of  $\geq 50\%$ ) in Stage 1 (including subjects who received the same dose during Phase 1 of the study), the study will be terminated if  $\leq 1$  subject responds. If the study progresses to Stage 2, an additional 7 subjects will be treated, for a total of up to 16 evaluable subjects per dose cohort. If at least 5 subjects respond out of the total 16 within a dose cohort, there will be demonstration of efficacy of ONCT-534 within the population for this dose cohort and the corresponding null hypothesis will be rejected. Additional subjects may be enrolled to account for unevaluable subjects.

Randomized dose assignment will proceed when both cohorts are open for enrollment. If one of the dose levels is closed due to safety findings or lack of efficacy, or is paused until Stage 1 efficacy is observed, non-randomized assignments may proceed within the open dose level expansion cohort.

The expected maximum sample size in Phase 2 is 32.

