### 9.5.3. Analysis of PSA Levels

PSA50 is defined as the earliest attainment of a  $\geq 50\%$  decline in PSA relative to the baseline PSA obtained during the Screening period. The proportion of patients achieving PSA50 and time to PSA50 will be reported.

PSA90 is defined as the earliest attainment of a  $\geq 90\%$  decline in PSA relative to the baseline PSA obtained during the Screening period. The proportion of patients achieving PSA90 and time to PSA90 will be reported.

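### A PSA50 reached on one dose can be credited to another dose's Phase 2 cohort, because the plan has no attribution rule for Phase 1 men who change dose

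*Combined protocol and SAP*

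**What the plan says.** Section 4.1.3 gives Phase 1 men two ways to change dose. After the DLT window they "will be offered the opportunity to escalate to a subsequent dose level that has been deemed safe by the SRC". Once the Phase 2 doses are chosen, "Phase 1 subjects continuing treatment will be offered the opportunity to be randomly assigned to one of these Phase 2 doses", if the investigator agrees. The synopsis says the same.

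Section 9.5.3 measures response as a "decline in PSA relative to the baseline PSA obtained during the Screening period", and the definition starts "PSA50 is defined as the earliest attainment of a". Table 1 has a single Screening column. No section resets the baseline at a dose change or ties a PSA50 to the dose being taken when it was reached.

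Three provisions bear on who is counted:

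- Section 9.1.2: "A total of 9 subjects per dose level will be randomly assigned in Stage 1".
- Section 9.5.2 evaluates the first 9 subjects "including subjects who received the same dose during Phase 1 of the study". It does not limit this to men who started on that dose.
- Section 9.2 says of the Efficacy-evaluable Population: "Subjects will be grouped by dose received". For the Safety Population, by contrast: "Subjects will be grouped by the ONCT-534 dose received at study entry".

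**The concern.** The two-stage rule is meant to judge what a given dose does in men who start on it. Suppose a man reaches PSA50 at one level and then moves up, within Phase 1, to a level later chosen for Phase 2. He has received that dose during Phase 1, so Section 9.5.2 admits him to the first 9. His baseline is still the Screening PSA and his earliest attainment is already on record, so he is a responder before the new dose has had any effect. Section 9.2 does not prevent this: the entry-dose restriction written for safety is not applied to efficacy.

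A second route is open but less clear. A man re-randomized to a Phase 2 dose he has not taken before fits the randomly assigned description in Section 9.1.2, but no section says whether he belongs to the cohort.

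The Stage 1 gate needs only 2 responders, so a few such men could matter. Comparing the two doses and selecting one is a primary Phase 2 objective (Section 3.2), so crediting one dose with another's effect bears directly on the decision.

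**Working it through.** **Inputs from Sections 9.1.2 and 9.5.2.** Null rate 0.10; alternative 0.40; one-sided alpha 0.025; power 80%; continue if at least 2 of 9 respond; reject the null if at least 5 of 16 respond.

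**Step 1: reproduce the stated design.** Let X be Binomial(9, 0.1) in Stage 1 and Y be Binomial(7, 0.1) in Stage 2.

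- P(pass Stage 1) = 1 − 0.9⁹ − 9 × 0.1 × 0.9⁸ = 1 − 0.3874 − 0.3874 = 0.225.
- P(reject) = Σ over x ≥ 2 of P(X = x) × P(Y ≥ 5 − x). The terms are 0.1722 × 0.0257 = 0.0044 (x = 2), 0.0446 × 0.1497 = 0.0067 (x = 3), 0.0074 × 0.5217 = 0.0039 (x = 4) and 0.0009 (x ≥ 5). The sum is 0.0159.
- The same sum at 0.40 gives power 0.815.

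The stated design is therefore correct: type I error is 1.6% against the 2.5% limit, and power is 81.5%.

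**Step 2: add dose-changed men.** Let m of the first 9 be dose-changed men, each counted as a responder with probability q because of a PSA50 before the change. Everyone else responds at 0.10. With J as Binomial(m, q) and X as Binomial(9 − m, 0.1), Stage 1 passes if J + X ≥ 2, and the null is rejected if also J + X + Y ≥ 5. The documents give neither m nor q, so both are assumptions shown as a range.

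Example, m = 1 and q = 0.3. If the man is a prior responder, passing and rejecting have probabilities 0.570 and 0.0544; if not, 0.187 and 0.0116.

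- Pass: 0.3 × 0.570 + 0.7 × 0.187 = 0.302.
- Reject: 0.3 × 0.0544 + 0.7 × 0.0116 = 0.0244.

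Stage 1 passage / type I error at a true rate of 10%:

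| q | m = 1 | m = 2 | m = 3 |
|---|---|---|---|
| 0.1 | 22.5% / 1.6% | 22.5% / 1.6% | 22.5% / 1.6% |
| 0.3 | 30% / 2.4% | 38% / 3.6% | 46% / 5.2% |
| 0.5 | 38% / 3.3% | 55% / 6.3% | 69% / 11.0% |

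Here q is the man's whole chance of being counted. If a man without a prior PSA50 can still respond later with probability 0.10, his chance becomes q + (1 − q) × 0.10. At q = 0.3 that is 0.37, and type I error is 2.7%, 4.5% and 7.0% for m = 1, 2, 3. At q = 0.1 it is 0.19, giving 2.0%, 2.4% and 2.9%.

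**The case against.** The strongest objection is that the documents never say re-assigned men are Phase 2 enrollees. The heading of Section 4.1.3 places them under Phase 1, and its text still calls them Phase 1 subjects. Section 4.1.2 speaks of starting doses, and these men have already started. Inclusion criteria 9 and 10 require a washout and progression on or after the latest systemic treatment, which a man in PSA response on ONCT-534 would not meet if screened afresh. This stands as evidence of intent. A reader might infer that the plan counts re-randomized men in the 9 and 16; it does not say so. The objection does not reach men who escalated within Phase 1, whom the wording of Section 9.5.2 covers.

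A reader might also fix one, two or three inherited responders among the first 9 and quote false-success rates of 5.4%, 15.8% and 37.9%. The arithmetic is right, but it conditions on men already known to have responded. The same 5.4% applies to any ordinary subject once he has responded, and 0.1 × 5.44% + 0.9 × 1.16% returns 1.59%. Inflation requires dose-changed men to be counted as responders more often than 10% of the time. At a 10% rate, 27 Phase 1 subjects would yield about 2.7 responders in all, before discontinuations, declined offers and a split across two doses. Dose-changed non-responders would count against the new dose. The direction is therefore not certain, although Section 4.1.3 selects continuing, compliant men who tolerate the drug, which makes enrichment plausible.

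A third tempting inference is that these men would flatter tolerability at the new dose. Section 9.2 groups the Safety Population by entry dose, so the documents do not support it.

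Finally, Section 9.4 defers detail to the SAP. But the SAP need only be final before database lock, and the Stage 1 decision comes earlier, so the counting rule could be settled with responses already known.

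**Conclusion.** The point holds as a gap in the rules, not as a declared plan to count re-assigned men. As written, a PSA50 reached on an earlier dose can be credited to a Phase 2 cohort, most clearly for men who escalated in Phase 1 to a dose later chosen for Phase 2.

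The size is modest to material and depends on two unknowns. One dose-changed man at q = 0.3 leaves type I error just inside 0.025. Two or three at q = 0.3, or even one at q = 0.5, take it above. At q = 0.1, taken as the man's whole chance of being counted, there is no inflation. The sample-size calculation itself is sound. The sponsor should close the gap before the Stage 1 decision.

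**What to change.** State in Sections 4.1.3, 9.2 and 9.5.2 that a Phase 1 subject who escalated or was re-assigned to a Phase 2 dose after starting on a different dose does not count among the 9 or 16 of that cohort, and that his PSA50 is attributed to his first-assigned dose. Report his data after the change separately and descriptively. Deleting the same-dose clause in Section 9.5.2 would not be enough, because a re-randomized man would still fit the randomly assigned wording of Section 9.1.2.

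The cost is a few sentences of text. Reassignment can still be offered. The small downside is that these men do not fill Phase 2 slots, so accrual is not shortened.

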## 4.2. Scientific Rationale for Study Design

### 4.2.1. Rationale for Study Population

Next-generation ARSIs, such as enzalutamide, apalutamide, darolutamide, and abiraterone, initially provide most men with mCRPC with significant disease control and improved quality of life. However, resistance to therapy usually develops, and subsequent chemotherapy is associated with substantial toxicity. The most common reasons for resistance to AR-directed therapies include AR gene amplification, mutations in the LBD, and the expression of AR splice variants that lack part or all of the LBD (Krause, 2023). Therefore, there is an unmet clinical need for treatment of patients with advanced CRPC who have resistance to ARSIs by virtue of alterations of the AR.

ONCT-534 is a DAARI with a novel mechanism of action that includes inhibition of AR function and degradation of the AR protein mediated by interaction with the NTD of the AR. ONCT-534 has demonstrated preclinical activity in prostate cancer models against both unmutated AR, and against multiple forms of AR alteration, including those with AR amplification, mutations in the AR LBD, and splice variants with loss of the AR LBD. It has the potential to address significant unmet medical needs for men with mCRPC resistant or refractory to at least one next-generation ARSI, such as enzalutamide, darolutamide, apalutamide, or abiraterone, the population to be enrolled in this study.

### 4.2.2. Rationale/Justification of Starting Dose

The highest non-severely toxic dose (HNSTD) and no observed adverse event level (NOAEL) in dogs was identified as 10 mg/kg/day. The severely toxic dose to 10% of animals (STD10) and NOAEL in mice was identified as being greater than 60 mg/kg/day. Using body surface area (BSA) conversion and an average human BSA of 1.6 m^2, the dog HNSTD/NOAEL translates to a human starting dose of 54 mg/day (conversion factor of 1/6), and the mouse STD10/NOAEL translates to a human starting dose of 29 mg/day (conversion factor of 1/10). The starting dose will be the average of these 2 values, or 40 mg per day.

## 5. STUDY POPULATION

The Investigator or designee must ensure that only subjects who meet all the following inclusion and none of the exclusion criteria at Screening are offered treatment in the study.

### 5.1. Subject Inclusion Criteria

1. Subject has provided informed consent and has signed an approved consent form that conforms to all applicable regulations and institutional guidelines.
2. Subject is  $\geq 18$  years of age at the time the Informed Consent Form (ICF) is signed.
3. Subject has histologically documented metastatic adenocarcinoma of the prostate confirmed by biopsy without neuroendocrine differentiation or small cell features.
4. Subject has a history of mCRPC.

5. Subject has R/R disease following treatment with at least 1 next-generation ARSI, e.g., enzalutamide, apalutamide, darolutamide, or abiraterone. Subjects with symptomatic and/or extensive visceral disease should have had prior therapy with  $\geq 1$  taxane regimen, unless considered ineligible for treatment with a taxane (per the treating Investigator) or have refused treatment with a taxane.
6. Subject has at least one measurable lesion according to Response Evaluation Criteria in Solid Tumors (RECIST) v1.1 criteria or evaluable bony disease. Lesions that have been previously irradiated will be considered measurable only if progression has been documented following completion of radiation therapy.
7. Subject has an Eastern Cooperative Oncology Group (ECOG) performance status of 0 to 2 ([Appendix 1](#)), and life expectancy of  $\geq 6$  months.
8. Subject agrees to take or continue luteinizing hormone-releasing hormone (LHRH) agonist or antagonist therapy or has undergone bilateral orchiectomy.
9. At least 2 weeks or five half-lives have elapsed, whichever is earliest, since the subject's last systemic therapy, including taxanes or other chemotherapy. At least one month has elapsed since systemic therapy with radionuclide pharmaceutical agents.
10. Subject has evidence of disease progression on or after their most recent systemic treatment, defined by any of the following criteria:
  - a. Increasing serum PSA levels as defined by the Prostate Cancer Working Group 3 (PCWG3), determined by 2 consecutive measurements (compared with a baseline or nadir value), with at least 7 days between each PSA measurement; or
  - b. Progression of measurable disease by RECIST v1.1, or progression of bony disease as defined by PCWG3 criteria.
11. Subject has a PSA level  $\geq 10$  ng/mL, or  $\geq 2$  ng/mL and  $\geq 50\%$  increase from nadir on prior therapy, whichever is lowest.
12. Subject has serum testosterone  $< 50$  ng/dL.
13. Subject has adequate renal, hepatic, and pulmonary function, as determined by meeting the following criteria:
  - a. White blood cell count  $\geq 3,000$ /uL (No growth factors within 4 weeks).
  - b. Hemoglobin  $\geq 9$  g/dL (No transfusion within 4 weeks).
  - c. Creatinine clearance  $\geq 60$  mL/min using the Cockcroft-Gault Formula ([Appendix 1](#)).
  - d. Platelet count  $\geq 100,000$ /uL.
  - e. Serum alanine aminotransferase and aspartate aminotransferase (ALT/AST)  $\leq 2.5$  upper limit of normal (ULN).
  - f. Total bilirubin  $\leq 1.5$  ULN, or  $\leq 2.5$  ULN in subjects with Gilbert's syndrome.
14. Subject is committed to undertaking the following measures while being treated with ONCT-534 and for 3 months after the last dose of study drug:
  - a. Do not make semen donations; and
  - b. Unless documented to be surgically sterile (i.e., vasectomy, bilateral orchiectomy, or radical prostatectomy), practice true abstinence [when this is in line with the preferred

- and usual lifestyle of the subject] or use a highly effective method of contraception (e.g., condom and spermicide) with any female partner of childbearing potential.
- c. Request their partners of child-bearing potential use a method of highly effective contraception.

## 5.2. Subject Exclusion Criteria

A subject will be excluded from entering the study if any of the following criteria apply:

1. Subject has small cell prostate cancer or neuroendocrine disease histology, including mixed histology.
2. Subject has metastases to the brain or CNS.
3. Subject is receiving concurrent systemic anti-cancer therapies (including chemotherapy, antibody therapy, immunotherapy, cellular therapy, or other experimental therapies) except for ongoing androgen inhibiting therapy such as LHRH agonists. Supportive non-cancer directed therapies such as bisphosphonates or denosumab are allowed.
4. Subjects taking a strong inducer or inhibitor of CYP3A4 ([Appendix 3](#)), or a substrate of CYP3A4, CYP2C9 or CYP2C19 with a narrow therapeutic index ([Appendix 3](#)) are excluded unless the Investigator considers the medication essential with no alternatives available.
5. Subject had major surgery within 30 days prior to start of study drug.
6. Subject has current, untreated pathologic long-bone fractures(s), or risk of imminent pathologic fracture(s).
7. Subject has current or imminent spinal cord compression.
8. Subject has an active seizure disorder or a history of seizure disorder(s).
9. Subject has evidence of active human immunodeficiency virus (HIV), hepatitis B virus (HBV), or hepatitis C virus (HCV) infection. For further definition see Section [8.1.1.5](#).
10. Subject has any other serious illness or medical condition that would interfere with study participation, such as but not limited to:
  - a. Clinically significant, active cardiovascular disease: myocardial infarction or coronary artery bypass grafting within 6 months, unstable angina, congestive heart failure of New York Heart Association Classification Class III or IV ([Appendix 1](#)), or serious cardiac arrhythmia requiring medication.
  - b. Pulmonary disease requiring supplemental oxygen.
  - c. A known gastrointestinal condition that would limit the ingestion or gastrointestinal absorption of drugs administered orally.
11. Subject has abnormal ECGs that are clinically significant, including average QTcF > 450 ms, or a history of Torsade de Pointes.
12. Subject has any infection requiring parenteral antibiotic therapy or causing fever (temperature > 100.5°F or 38.1°C) within 1 week prior to first dose.

13. Clinically significant other malignancy with the potential to confound study assessments, with the exception of e.g., treated cutaneous squamous cell and basal carcinomas, non-muscle invasive bladder cancer, Rai Stage 0 chronic lymphocytic leukemia (CLL), and adequately treated Stage 1 to 2 non-cutaneous malignancy in remission for 5 years.
14. Subject is unable to comply with the protocol and/or not willing or not available for follow-up assessments.
15. Subject has any medical intervention or other condition which, in the opinion of the Investigator, could compromise adherence with study requirements or otherwise compromise the study's objectives.

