### 2.4.3. Assessment of Potential Risks and Benefits

ONCT-534 has not yet been administered to humans. Therefore, the overall assessment of potential benefit/risk is based on nonclinical findings from pharmacology studies, the definitive 28-day toxicity studies in mouse and dog, and risks described for other molecules in the class.

Since potential effects were observed in liver and kidney, subjects with moderate and severe renal or hepatic impairment will initially be excluded from the Phase 1/2 clinical study. In addition, all subjects will be monitored closely for changes in liver and kidney function in clinical studies with ONCT-534.

Considering the potential for other ARSIs to be associated with seizures, subjects with central nervous system (CNS) metastases or a history of seizure will initially be excluded from the study.

Overall, given the nature of the patient population and the limited number of subjects to be exposed in Phase 1 (n = 27) and Phase 2 (n = 32), clinical investigation of ONCT-534 is warranted in adult subjects with relapsed or refractory (R/R) histologically confirmed mCRPC resistant or refractory to at least one next-generation ARSI.

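### Section 2.4.3 says a history of seizure is excluded, but exclusion criterion 8 covers only an undefined seizure disorder, so a past isolated or provoked seizure need not exclude a subject

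*Combined protocol and SAP*

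**What the plan says.** Section 2.4.3 (Assessment of Potential Risks and Benefits) refers to the seizure risk of other ARSIs and states that "subjects with central nervous system (CNS) metastases or a history of seizure will initially be excluded from the study". The sentence names two groups: men with CNS metastases and men who have had a seizure.

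Section 5 decides who is dosed. It says the investigator "must ensure that only subjects who meet all the following inclusion and none of the exclusion criteria at Screening are offered treatment". In Section 5.2 the two groups appear as follows:

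- Criterion 2: "Subject has metastases to the brain or CNS".
- Criterion 8: "Subject has an active seizure disorder or a history of seizure disorder(s".

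The reason for the exclusion is in Section 2.4.1, which reports seizures in 0.4% to 0.6% of patients on apalutamide, enzalutamide and darolutamide, and in 2.2% of enzalutamide patients with predisposing factors. Inclusion criterion 5 requires prior exposure to this kind of drug: "Subject has R/R disease following treatment with at least 1 next-generation ARSI".

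**The concern.** A seizure is an event; a seizure disorder is ordinarily a diagnosis. Section 2.4.3 excludes on the event, while both limbs of criterion 8 require the disorder. Sites enroll on criterion 8, so the protection described in the risk assessment is wider than the one that will be applied.

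Two consequences follow. Sites may treat the same history differently, one reading the undefined term to include a single seizure and another not. Also, a subject whom the benefit-risk argument assumes to be excluded could receive a drug never before given to humans. A seizure on an earlier ARSI is a plausible history in this population. The eligibility exclusion is the only preventive measure in the protocol aimed specifically at seizures. The dose-limiting toxicity definition (Section 8.3.7) and the dose modification rules (Table 2) are general and act only after an event.

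**Working it through.** The main check is a comparison of texts. The protocol states no figure on this point to reproduce.

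**1. Scope of the two statements**

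| History | Section 2.4.3 | Section 5.2 |
|---|---|---|
| CNS metastases | Excluded | Excluded (criterion 2) |
| Active or past seizure disorder | Excluded, as a history of seizure | Excluded (criterion 8) |
| One isolated or provoked seizure, no diagnosed disorder | Excluded | Not required by criterion 8 on its plain reading |

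The first group in the Section 2.4.3 sentence is carried over in full, the second only in part.

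**2. Is the term defined elsewhere?** No. Section 5, Section 8.1.1, the abbreviations list and the appendices give no definition. Criterion 11 in the same list uses an event-based history (Torsade de Pointes), so a site could reasonably take the word disorder in criterion 8 as deliberate.

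**3. Does another criterion close the gap?**

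- Criterion 4 with Appendix 3 reaches subjects now taking certain antiepileptic drugs, such as carbamazepine, phenytoin, phenobarbital, primidone or valproic acid. A man with one past seizure may take none of these. The criterion also has an exception: such subjects "are excluded unless the Investigator considers the medication essential with no alternatives available".
- Criterion 10 (serious illness that would interfere with participation) and criterion 15 (investigator's opinion) permit exclusion but do not require it, and neither names seizure.

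**4. Does the word initially in Section 2.4.3 explain the difference?** No. The Section 5.2 criteria are the initial criteria, and no later relaxation is described.

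**5. How other exclusions from Section 2.4.3 are carried over.** The same section says "subjects with moderate and severe renal or hepatic impairment will initially be excluded from the Phase 1/2 clinical study". For renal function, Section 5.1 turns this into a number, a creatinine clearance of at least 60 "mL/min using the Cockcroft-Gault Formula". For hepatic function it sets limits on ALT/AST and total bilirubin. The protocol does not define moderate or severe impairment, so this shows only that those exclusions became explicit thresholds. The seizure exclusion became an undefined term.

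**6. Illustration of size, one route only**

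Inputs: 27 Phase 1 and 32 Phase 2 subjects (Section 2.4.3); seizure rates of 0.4% to 0.6% on the three named drugs (Section 2.4.1). Assumption: every subject previously took one of those drugs and had a seizure at that rate.

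- Planned subjects: 27 + 32 = 59.
- Expected number with such a seizure: 59 × 0.004 = 0.236; 59 × 0.006 = 0.354.
- Chance of none, (1 − p)^59: 0.996^59 = 0.789; 0.994^59 = 0.701.

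This is not an estimate of the total. Subjects who had only abiraterone would lower it, and so would any whose seizure led to a diagnosed disorder already caught by criterion 8. Isolated seizures from other causes would raise it, but the protocol gives no rate for them.

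**The case against.** The strongest reply is that the exclusion exists and only its edge is in dispute. Section 2.4.3 is a one-sentence narrative, and its phrase may simply be shorthand for criterion 8. Nothing in the protocol proves that the sponsor intended the wider version. The inconsistency could also be removed the other way, by defining seizure disorder and narrowing Section 2.4.3. A rule covering any past seizure, with no time limit and no distinction between provoked and unprovoked events, would turn away some men with a remote single seizure.

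The practical stakes are also limited. The 28-day mouse and dog studies showed no seizurogenic potential (Section 2.2.3), and the suggestion of brain penetration rests on mouse data (Section 2.2.2). Abiraterone alone satisfies inclusion criterion 5, and the seizure statement in Section 2.4.1 does not name it. Convulsions are listed in Section 8.3.6 as an example of an event usually considered serious, SAEs are reported within 24 hours, and the Safety Review Committee sees cumulative safety data.

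The limits on size stand: few subjects are likely to be affected, quite possibly none. The reporting and review safeguards work only after a seizure. That some sites may read criterion 8 broadly does not rescue it, since differing readings are themselves a fault in an eligibility rule. Narrowing Section 2.4.3 would make the texts agree, but only by withdrawing a protection that the benefit-risk assessment states.

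**Conclusion.** The concern holds. Section 2.4.3 and criterion 8 differ in scope, criterion 8 governs enrollment, and no mandatory criterion makes up the difference. The conclusion rests on reading seizure disorder as something more than a single seizure; a site that reads it otherwise would apply the wider rule.

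This is a safety and consistency point. It does not touch the sample size, the error rates or any analysis. The total number of subjects involved is not estimable from the protocol and is probably small. The prior-ARSI illustration, with its assumption that all 59 subjects took one of the three named drugs, makes none the likeliest outcome for that route. It should be corrected because the trial is first-in-human and the sponsor has already stated the wider exclusion.

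**What to change.** In Section 5.2, extend the second limb of criterion 8 by inserting the words *seizure or*, so that it covers a history of seizure or of seizure disorder(s). Leave the active-disorder limb and Section 2.4.3 as they are. The enrollment rule then applies the stated mitigation, and sites no longer have to interpret an undefined term.

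The cost is one line of text and the loss of a few otherwise eligible candidates, including some with remote seizures. No new procedure is needed, because medical history is already collected for eligibility at Screening (Section 8.1.1.3).

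If the sponsor did intend the narrower rule, it should define seizure disorder in Section 5.2 and correct Section 2.4.3 to match, recognizing that this gives up part of the stated protection.
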